The Magstim TMS BISTIM (used at CCHMC since 2001) and Rapid2 Stimulators (used at CCHMC since 2008) are approved in the United States for peripheral nervous system stimulation, but not for routine clinical diagnostic or therapeutic central nervous system

applications at this time. Many neurophysiology laboratories, including ours, have used TMS as a non-invasive technique to measure neurophysiological properties of the central nervous system in children. TMS is ideal for studying the motor system, but has other applications as well. It is well tolerated by most children, with minimal or no discomfort. In our prior IRB-approved studies, we have used series TMS to study motor cortex physiology in healthy children as well as children with Tourette Syndrome and Attention Deficit Hyperactivity Disorder (ADHD).

V. PRELIMINARY DATA IN CHILDREN

For the scenarios above and described in Table 1, we do not have preliminary data. This study is exploratory. However, we are currently using TMS as part of an NIMH-funded study to understand motor development in typical and ADHD children (CCHMC 06 10 35). In this ongoing study of ADHD vs. typical children between the ages of 8 and 12 years, we do have some data that might be useful for comparison. For example, motor threshold correlates highly with age: $r = -.63$, $p < .001$; $n = 72$ children (preliminary analysis, data unpublished, study ongoing). The mean threshold is 68% of maximal stimulator output, and the Standard Deviation is 16%.

VI. RESEARCH PLAN

1. Number of subjects and methods of selection:

- i. For this study, we are requesting permission to recruit up to 300 children and adults at CCHMC.
- ii. Study eligibility will be determined by the principal investigators [name] or [name] in consultation with the managing physician, based on presence of motor system problems described in Table 1.

2. Inclusion and Exclusion criteria:

Inclusion Criteria

- i. Either gender, any race, ethnicity or socioeconomic status
- ii. Children greater than 2 years old and adults less than 60-years old with diseases affecting the motor system and interfering with voluntary movement. Adult diseases would typically have childhood onset, e.g. spinocerebellar ataxia, degenerative leukodystrophies, spinal cord disease.
- iii. Healthy individuals recruited for comparative normative data.

Exclusion Criteria

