- i. Standard contraindications to TMS: Implanted brain stimulator, vagal nerve stimulator, VP shunt, aneurysm clip, cardiac pacemaker, or implanted medication port.
- ii. Other situations where it is reasonable to avoid TMS: Pregnant females or sexually active females not using birth control. Significant medical conditions including kidney disease, anemia, thyroid disease, lung disease, heart disease. In

addition, any conditions, in the judgment of the investigators, for which external magnetic stimulation might risk harm.

3. Randomization:

NA

4. Study Procedures:

Prior to participation, parents will sign consent forms and children older than 11 years will sign assent forms.

Participation in this study and use of TMS will not in any way influence standard medical care, in order to minimize coercion.

Diagnostic information obtained through this study is not part of standard medical care and will not be available to clinicians.

This study has 4 parts, listed here and described in greater detail below:

1. Collection of routine clinical data obtained during standard of care evaluations in children with neurological conditions.
2. Administration of TMS as described in Table 1 and in the clinical scenarios above.
3. Data storage, analysis, comparison with prior CCHMC and published data.
4. Use of data for hypothesis generation, effect and sample size calculations for future studies.

Routine Clinical Data Acquisition

Clinical and demographic information will be obtained after informed consent. This information will include diagnosis, results of imaging, laboratory, or neurophysiological studies as appropriate. When appropriate, the following clinical rating scales may be used – Yale Global Tic Severity Scale ²⁴, Premonitory Urge Rating Scale ²⁵, Children’s Yale-Brown Obsessive Compulsive Scale ²⁶ and DuPaul ADHD Rating Scale ²⁷.

TMS – details:

TMS will be performed using a Magstim 200® stimulator (Magstim Co., New York, NY, USA) connected through a Bistim® module to a TMS coil as described in CHMC 06-10-11; 05-05-19; 03-05-52; 03-05-53. A 70 mm double cone coil will be used for lower limb stimulation – see below. Currently the lab has 90 mm circular, 70 mm figure-8 and 40 mm figure 8 coils.

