VIII. POTENTIAL BENEFITS

There is a potential for direct benefit by participating in this study if the clinical neurophysiological information is useful to the managing physician.

IX. POTENTIAL RISKS, DISCOMFORTS, INCONVENIENCES, AND PRECAUTIONS

1. Known and potential discomforts or hazards of single and paired pulse TMS:
Single and paired pulse TMS has been used at CCHMC under [name] direction since 2001 for research only. Potential discomforts are mild and transient. In a prior study of 40 healthy and ADHD children, Garvey et al asked children to rank TMS compared to other childhood activities. TMS was ranked preferable to 1) a "shot"; 2) going to the dentist; and 3) a long car ride ⁴³. The following mild, transient effects were reported in our prior study of 35 children and adults: scalp discomfort (12%), hand weakness (9%), headache, neck pain, arm pain, and arm tingling (6%), hand pain, decreased hand dexterity, hearing changes, and tiredness (3%). All of these had resolved by the following day. There were no physical findings after TMS supporting the subjective descriptions of loss of strength or dexterity. Furthermore, a consensus statement from the international TMS community concluded that "single-pulse and paired-pulse TMS in pediatrics is safe for children two years and older."⁴⁴ A prior common concern about use of TMS was the risk of seizures⁴⁵. We follow recommended guidelines ⁴⁵ and have seen no seizures in children or adults studied at our center. In addition, more recent studies even in children with epilepsy suggest that the risk of TMS inducing seizures is quite low.

2. Precautions, risk minimization:

The protocols include a number of precautions to minimize risk. The TMS laboratory was established in 2001 in consultation with [name], an internationally known researcher in transcranial magnetic stimulation. [name] or [name] will be present during TMS. All subjects will wear 34 NRR earplugs or headphones during TMS if the head is stimulated at an intensity of over 90%. Standard exclusion criteria are applied for participation in this study. Detailed questioning for any adverse events will occur after the experiment and the next day after the study.

3. The method of monitoring study conduct.

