Adverse events will be reviewed using direct questions with a detailed review of systems on the day of the study and by phone the next day. The principal investigator is responsible for reporting adverse events to Cincinnati Children's Hospital Medical Center Institutional Review Board.

4. Methods for maintaining data quality and confidentiality:

Data are maintained in case report folders identified only by an anonymous subject ID, in the locked principal investigator's office which is situated in a locked office suite. All data kept in computerized files are in computers or a server with restricted, password-protected access.

5. An assessment of accrual (timely enrollment) and the handling of dropouts.
Accrual rates will be monitored by the principal investigator.

7. Data Safety Monitoring Plan:

The data safety monitoring plan is to review adverse events at weekly meetings of the TMS research group.

X. PROPOSED RISK BENEFIT ANALYSIS

In the opinion of the investigative team, this study, based on our experience administering TMS as well as the published literature on TMS, involves minimal risk, with potential for direct benefit.

XI. SECURITY/CONFIDENTIALITY

Privacy of the individuals participating in this proposed study will be maintained through non-identifying subject ID codes, locked storage and password protected files. The study log will be maintained in a password protected folder on the desktop computer of the principal investigator. Case reports and spreadsheets will refer to subjects by number only. Subjects will be informed that, if necessary, the IRB or FDA may review the data.

XII. DURATION

We estimate the proposed study to take 6 years to complete.

XIII. FUNDING

Movement Disorders Research Fund.
Tourette Association of America until 4/30/2020.

XIV. PAYMENT FOR STUDIES

There will be no charges to patients or to third party payers related to participation in this study. Subjects will be paid \$15/hour (prorated) for completing this study.

Payment will be in the form of a reloadable debit card (ClinCard). We will provide the card and load money onto the card after each completed visit based on the schedule listed above. We will also administer a handout that will explain how to use it.

Because this research study involves payment for participation, we are required by federal Internal Revenue Service (IRS) rules to collect and use participants' social

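### The protocol sets no same-day symptom baseline before TMS, so in participants whose disease already causes weakness, clumsiness, sensory symptoms or pain, attributing such complaints to TMS is unreliable

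*Combined protocol and SAP*

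**What the plan says.** Two places govern how adverse events are found. Section IX.2 gives the timing: "Detailed questioning for any adverse events will occur after the experiment and the next day after the study". Section IX.3 gives the method: "direct questions with a detailed review of systems on the day of the study and by phone the next day". IX.3 does not place the study-day review before or after stimulation.

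Inclusion criterion ii in section VI.2 admits children and adults with "diseases affecting the motor system and interfering with voluntary movement". Criterion iii adds a second group: "Healthy individuals recruited for comparative normative data". Table 1 lists the eligible conditions. They include stroke, cerebral palsy, transverse myelitis, plexus injury and Guillain-Barre syndrome, and also tic, Tourette syndrome and stereotypy.

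The routine clinical data in section VI.4 are described as follows: "This information will include diagnosis, results of imaging, laboratory, or neurophysiological studies as appropriate". The optional rating scales cover tics, premonitory urge, obsessive-compulsive symptoms and ADHD. Section VI.5 lists no questionnaires, and section VI.3 gives randomization as not applicable.

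Section IX.1 reports effects from the laboratory's earlier study of 35 children and adults. Among them are hand weakness (9%), arm tingling, arm pain and neck pain (6%), and hand pain and decreased hand dexterity (3%). It then states: "There were no physical findings after TMS supporting the subjective descriptions of loss of strength or dexterity".

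**The concern.** The complaints that TMS is known to produce overlap with the complaints that bring many of these patients into the study. If a child with a plexus injury reports a weak hand after the session, the report means little unless someone recorded how the hand was just before it.

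The earlier work described in section IV was in healthy children and children with Tourette syndrome or ADHD, where the overlap is small. This protocol carries the same style of questioning into groups where it is large.

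The weekly adverse event review and the reporting of events to the IRB (section IX) are at stake. So is any description of how well patients with motor disease tolerate TMS, in a study that presents itself as one of feasibility and expects to publish some of its data. A standing deficit may be recorded as an event, or a real worsening may be put down to the disease. A baseline not taken before the first pulse cannot be recovered later.

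**Working it through.** The plan gives no figure to reproduce. The ceiling of 300 participants has no formula behind it, and no adverse event rate is set as an endpoint. The check is mainly one of setting the sections side by side.

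**Step 1: is there a pre-stimulation symptom record anywhere?**
- IX.2 puts the questioning after the session and on the next day.
- IX.3 has a study-day review with no stated position relative to TMS. Its purpose is to review adverse events, and its two time points match those of IX.2.
- VI.4 collects diagnosis and test results, which are not tied to the day of TMS. None of its optional scales measures weakness, dexterity, tingling or pain.
- The physician-to-physician discussion in section XV takes place at referral.

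No section requires a same-day symptom record before stimulation.

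**Step 2: can anything else substitute?** There is no randomization, and no sham session is described. IX.1 refers to physical findings after TMS in the earlier study, but this plan specifies no examination before and after stimulation.

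**Step 3: who is affected?** Participants whose disease already produces the listed complaints are affected. Healthy participants are not. Those with tics or Tourette syndrome are affected less, because weakness or tingling need not be their presenting problem.

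**Step 4: illustration of size.** Inputs:
- *a* = 0.09, the hand weakness rate in IX.1 (about 3 of 35 people), taken as the rate of new weakness among those free of it beforehand.
- *p* = proportion already weak before TMS. The documents do not give this; 0.20, 0.50 and 0.80 are assumptions.
- Pre-existing and new weakness are assumed independent, and every standing deficit is assumed to be recorded as an event.

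Apparent rate = 1 − (1 − *p*)(1 − *a*). Share of reports that are new = *a*(1 − *p*) / apparent rate.

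| *p* | Apparent rate | Share that is new |
|---|---|---|
| 0 | 1 − 1.00 × 0.91 = 9.0% | 100% |
| 0.20 | 1 − 0.80 × 0.91 = 27.2% | 0.072 / 0.272 = 26% |
| 0.50 | 1 − 0.50 × 0.91 = 54.5% | 0.045 / 0.545 = 8% |
| 0.80 | 1 − 0.20 × 0.91 = 81.8% | 0.018 / 0.818 = 2% |

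At *p* = 0.50 the share that is new is 0.030 / 0.530 = 6% for tingling (*a* = 0.06) and 0.015 / 0.515 = 3% for dexterity (*a* = 0.03). The apparent rate is driven mostly by the assumed *p*. The table shows how the problem grows with baseline symptoms and vanishes without them; it does not forecast what this study would record.

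**The case against.** A reader might infer that adverse events are asked about only after TMS. The documents do not go that far. IX.3 leaves the time of the study-day review open, so a review before stimulation is not excluded. What stands is that none is required.

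A reader might also infer that TMS effects cannot be told from disease at all, so that every positive answer must be either counted or dismissed. That is too strong. The investigators settle eligibility with the managing physician, the condition is discussed at referral, and the diagnosis is on file. Direct questions can ask whether a symptom is new or worse. The next-day call also helps, since the effects in the earlier study had all resolved by then. These means are real but weaker than a recorded baseline. The protocol does not require the new-or-worse question or define an adverse event by it, and the answer would depend on recall, sometimes by young children. A complaint that persists at the call could be standing disease or a lasting effect.

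It is also fair to say that the registered title concerns Tourette syndrome, where the problem is small, and that section VI.8 plans no formal analysis and disclaims a case-control design. The point therefore cannot rest on a spoiled comparison of event rates between patients and healthy participants, or with the 35-person study. It rests on attribution in the ongoing safety review, which is needed whether or not rates are compared. The investigators judge the study to be of minimal risk and the earlier effects were mild, which limits the urgency but does not supply the missing baseline.

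**Conclusion.** The point holds in limited form, as something that should be changed. The protocol sets no same-day symptom baseline before TMS. In participants whose disease already causes weakness, clumsiness, sensory symptoms or pain, attribution of those complaints is unreliable, though not impossible. The size of that subgroup is not stated, since the protocol admits every Table 1 condition.

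The figures of about 27%, 55% and 82% hold only under the assumed prevalences, independence, transfer of the 9% rate to these patients, and the recording of every standing deficit as an event. No section says staff would record events that way. The conclusion rests on the comparison of sections and does not depend on those figures.

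**What to change.** In IX.2 and IX.3, ask the same review-of-systems items (weakness, dexterity, tingling, pain, headache, hearing, tiredness) at three times: immediately before the first pulse of each visit, after the session, and at the next-day call. Define an adverse event as an item that is new or worse than the pre-pulse answer. Summarise events separately for patients and healthy participants. State in IX.3 when the study-day review takes place.

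The cost is a few minutes per visit with the same questions and staff, one more column on the adverse event form, and a short amendment. No stimulation procedure changes.
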